#### **9.1.4.1.2. Infusion Set Changes**

The eCOA system will be used by patients to collect all infusion set changes, including date and time of change, designation of routine or premature change, primary reason for premature change (infusion set kinked, came out, or leaking; empty pump reservoir; infusion site pain or redness; pump occlusion alarm; suspected infusion set occlusion; other).

In the case of suspected infusion set occlusion, patients will choose or enter a new correction bolus from the eCOA diary that corresponds to the time of the suspected occlusion. They will then indicate if the correction bolus was given via pump or via syringe. If more than one correction bolus is given, patients should choose the first non-meal related correction bolus. This information is also critical in order to evaluate the primary objective of the study.

Investigators will review pump occlusion alarms, suspected infusion set occlusions, and premature infusion set changes with patients at each visit.

Any interruption of CSII will need to be documented in the eCRF. When patients resume use of pump following the interruption, the infusion set insertion should be entered as “routine” infusion set change in eCOA.

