**9.1.4.2. Troubleshooting Unexplained Hyperglycemia**

Investigators will review unexplained hyperglycemia troubleshooting and management with patients at Visit 2 and may repeat as necessary at subsequent visits. Troubleshooting guidelines for unexplained hyperglycemia management will be provided as a tool for patient use. A blood ketone meter and test strips will be provided to each patient to aid in hyperglycemia management. All episodes of unexplained hyperglycemia >250 mg/dL should be confirmed by SMBG using the study glucometer. Patients should check to ensure the pump is in place, the prior bolus dose was delivered, and the infusion set is in place without any leaks or kinks in the system. All non-meal-related correction boluses including date, time, and dose should be entered into eCOA. Glucose response to the correction bolus should be confirmed by SMBG in approximately 1 hour. Blood ketones should be tested with the meter provided when unexplained hyperglycemia occurs with blood glucose >250 mg/dL (13.9 mmol/L) or a pump occlusion alarm occurs with blood glucose >250 mg/dL (13.9 mmol/L). If blood ketones are positive (>0.6 mmol/L) or nausea and/or vomiting is present, the patient should inject the correction dose by syringe, change the insulin, reservoir, and infusion set, and continue to monitor BG every 1 to 2 hours until within range. If BG is not responding to correction and/or signs of DKA are present, the patient should go immediately to the nearest emergency room.

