5.1. Summary of Study Design

Study I8B-MC-ITSI is a Phase 3, prospective, randomized, double-blind, outpatient, multinational, multicenter, 2-treatment group, crossover, active-controlled study conducted in patients with type 1 diabetes (T1DM) currently using CSII. In the 2 treatment groups, LY900014 and insulin lispro, meal bolus doses will be delivered immediately prior to each meal (0 to 2 minutes) in a double-blind manner.

The study includes a 1-week screening period and a 2-week lead-in period followed by a 2-period (Period I and Period II) crossover and a 4-week post-treatment safety follow-up. Each period of the crossover will consist of 6 weeks of treatment with no washout between periods.

Figure ITSI.5.1 illustrates the study design.

[figure not shown]

Figure ITSI.5.1. Illustration of study design for Clinical Protocol I8B-MC-ITSI.

Patients who need to discontinue from study treatment will also be discontinued from the study. Please refer to Protocol Sections 8.1 and 8.2. In this document, discontinuation of IP refers to the last dose of IP in a study period (lead-in, Period I, or Period II).

The eCOA diary will be used by patients to document 4-point SMBGs (consists of fasting [pre-morning meal], pre-midday meal, pre-evening meal, and pre-bedtime), hypoglycemia, and all infusion set changes, including date and time of change, designation of routine or premature change, primary reason for premature change (infusion set kinked, came out, or leaking; empty

pump reservoir; infusion site pain or redness; pump occlusion alarm; suspected infusion set occlusion; other) as depicted in Protocol 9.1.4.1. Additional data on infusion site complications will be collected by investigators.

Patients will enter all non-meal-related correction boluses into the eCOA diary. In the case of suspected infusion set occlusion, patients will choose or enter a new correction bolus from the eCOA diary that corresponds to the time of the suspected occlusion. They will then indicate if the correction bolus was given via pump or via syringe. If more than one correction bolus is given, patients should choose the first non-meal related correction bolus. This information is also critical in order to evaluate the primary objective of the study.

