- ¹ Daytime: 0600 hours to midnight (06:00:00-23:59:59 on the 24-hour clock).
- ² Nighttime: midnight to 0600 hours (00:00:00-05:59:59 on the 24-hour clock).
- ³ Breakfast is defined as the first “Carbs” event between 4 AM and 11 AM that is associated with an “Insulin” event within ±30 minutes.
- ⁴ All eCOA non-meal related correction doses excluding those confirmed as delivered via syringe for an unexplained hyperglycemia that leads to infusion set change, will be those delivered via the pump.
- ⁵ Time in ranges within 0-1 hour and 0-2 hours after breakfast
- ⁶ Overall variability refers to the variability calculated based upon all the CGM measurements collected across all valid days for each derivation period (e.g. 4-6 weeks relative to the start of each of the randomized treatment period).

To assess the glucose control over the course of approximately 72-hours of continuous insulin infusion, the duration and percentage of time in ranges (target, hypoglycemia or hyperglycemia)

and incremental AUCs after breakfast, will be derived based upon the CGM raw data collected on each of the infusion set catheter dwell days, including Day 1 (<0 and ≥ 24 hours), Day 2 (<24 and ≥ 48 hours) and Day 3 (<48 and ≥ 72 hours), and summarized by treatment group.

The glucose reduction rate and duration of each individual hypoglycemia episode will be analyzed by an MMRM model. The MMRM model will include the fixed effects of treatment, period, and sequence as fixed effects and patient as a random effect.

The glucose reduction rate and duration of each hypoglycemia episode will be analyzed by an MMRM model. The MMRM model will include the fixed effects of treatment, period, and sequence as fixed effects and patient as a random effect.

Hypoglycemia/hyperglycemia rates as measured by CGM data will be summarized for 30 days and 1 year / 100 years (hypoglycemia <50 mg/dl and hyperglycemia >300 mg/dl only). The rate of hypoglycemia and hyperglycemia will be compared between treatment groups using Wilcoxon signed-rank test.

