9.3. Interstitial Glucose Reduction Rate following a Correction Bolus via the Pump

The interstitial glucose reduction rate (mg/dl per minute and mg/dl per minute per unit of insulin dose) within 4 hours following a non-meal-related correction dose via the pump will be calculated by dividing the interstitial glucose reduction by the time it takes to first recover (≤ 180 mg/dL) from hyperglycemia after the correction dose. The interstitial glucose reduction rate will also be analyzed by sub-intervals of interstitial glucose levels at the time of the non-meal-related correction bolus: 180 to 250, 250 to 300, and >300 mg/dL (10 to 13.9, 13.9 to 16.7, and >16.7 mmol/L). The interstitial glucose levels at the time of the non-meal-related correction bolus, is defined as the most recent interstitial glucose within 1 hour prior to the correction bolus.

The non-meal related correction boluses delivered by pump will be derived through the following steps:

- Step 1: pull all correction boluses captured in eCOA;
- Step 2: exclude those correction boluses delivered through syringe;

- Step 3: exclude those associated with the last prior SMBG within 1 hour ≤ 180 mg/dl and the last post SMBG within 2 hours increases from prior SMBG. These correction boluses should not have been reported as non-meal related;
- Step 4: remove duplicate correction boluses. If 2 correction boluses are reported for the exact same time, only 1 correction bolus will be included;
- Step 5: if within 4 hours a second correction bolus is given before recovery (≤ 180 mg/dl), only the first non-meal-related correction bolus time will be used and the data after the second correction bolus will be censored. If the glucose never recovered to ≤ 180 mg/dL within 4 hours before any other correction boluses are given, the glucose reduction rate will be calculated by dividing the greatest glucose reduction within 4 hours before any other correction bolus, by the time it took to reach this level.

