9.11. Highest Postprandial Glucose

9.11.1. Time to the highest postprandial glucose within 3 hours after Meals

Time from start of meal to the highest postprandial glucose level will be calculated as the time from start of meal to the maximum glucose value within 3 hours after meals, excluding the data from patients who have had the next Carb or Insulin event.

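### SAP 9.3 does not end the 4-hour glucose reduction window at an infusion set change or a following meal, and leaves unclear whether a syringe dose ends it (cheap improvement)

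*SAP*

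**What the plan says.** SAP 9.3 builds the endpoint in five steps. Step 1 takes every correction bolus in the eCOA diary. Step 2 is to "exclude those correction boluses delivered through syringe". Step 3 drops some boluses that look meal-related, and Step 4 drops exact-time duplicates. Step 5 deals with a second correction before recovery: "only the first non-meal-related correction bolus time will be used and the data after the second correction bolus will be censored". If glucose never reaches 180 mg/dL or below, the numerator is "the greatest glucose reduction within 4 hours before any other correction bolus", divided by the time taken to reach that level.

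Four other places bear on this:

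- **Route of delivery.** A note to Table ITSI.6.8 (SAP 6.12) defines pump-delivered doses as "All eCOA non-meal related correction doses excluding those confirmed as delivered via syringe for an unexplained hyperglycemia that leads to infusion set change". The diary asks for route only for the bolus linked to a suspected occlusion, and Protocol 9.1.4.1.2 adds: "If more than one correction bolus is given, patients should choose the first non-meal related correction bolus".
- **Rescue.** Protocol 9.1.4.2 foresees cases in which "the patient should inject the correction dose by syringe, change the insulin, reservoir, and infusion set".
- **Off-pump exclusion.** SAP 9.2 limits CGM derivations to time on pump and on study insulin. SAP 5.1 says a syringe correction taken while still on the pump is not a pump interruption.
- **Meals.** Protocol 9.1.4.1.1 keeps meal boluses, and corrections combined with them, out of the correction log. For postprandial peaks, SAP 9.11.1 works by "excluding the data from patients who have had the next Carb or Insulin event". SAP 9.3 has no counterpart.

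**The concern.** The endpoint is meant to show how fast a correction bolus given through the pump lowers glucose. Censoring at a second correction bolus keeps later insulin out of that measurement. The same reasoning applies to two events that Step 5 does not name.

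The first is an infusion set change. A hyperglycemia-type primary event (SAP 6.11.1) requires a pump correction bolus at least 1 hour before the change, with no SMBG decrease by 1 hour (+10 minutes). If that change falls inside the 4 hours and CGM glucose is still above 180 mg/dL, later recovery through the new set is credited to the bolus that failed. If set failures differ by treatment, which is the trial's primary question, the error differs by treatment too.

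The second is a meal with its bolus. Postprandial behaviour is where the Protocol's rationale expects the two insulins to differ, so this contamination need not cancel within patient.

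For syringe doses, two programmers could apply Steps 2 and 5 differently and both claim to follow the text.

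**Working it through.** **Inputs.** The documents give no correction-bolus count, SD or expected rate for endpoint 6, so there is no plan figure to reproduce. The one sample-size calculation, 42/(1 − 0.12) = 47.7, rounded up to 48, does not involve this rule. All glucose values below are assumptions for illustration.

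**Step 1: which events end the window?**

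| Event after the index bolus | Ends the window? | Basis |
|---|---|---|
| CGM at or below 180 mg/dL | Yes | SAP 9.3 |
| 4 hours elapsed | Yes | SAP 9.3 |
| Second correction logged, not tagged as syringe | Yes | SAP 9.3 Step 5; Table ITSI.6.8 note |
| Second correction tagged as syringe | Unclear | Step 2 removes it first; Step 5 sets no limit on route |
| Infusion set change | No rule | SAP 9.3; not an interruption as SAP 5.1 defines it |
| Meal or meal bolus | No rule | Outside the correction log |

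**Step 2: failed set.** Assume 280 mg/dL at the bolus and 285 at 70 minutes, then a set change with no censoring bolus, then a steady fall of s mg/dL/min. Time to 180 is 70 + (285 − 180)/s, and the score is (280 − 180)/time.

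| s | Time to 180 (min) | Score, window open (mg/dL/min) |
|---|---|---|
| 0.75 | 210 | 0.48 |
| 1.0 | 175 | 0.57 |
| 1.5 | 140 | 0.71 |
| 2.0 | 122.5 | 0.82 |

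Closed at 70 minutes, the greatest change is 280 − 285 = −5 mg/dL, so there is no fall. SAP 9.3 does not say how such a window scores.

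**Step 3: meal at 60 minutes.** Assume 240 mg/dL at the bolus and 210 at the meal.

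- Closed at the meal: 30/60 = 0.50.
- Open, no post-meal rise, then a fall of 1 mg/dL/min: 60/(60 + 30) = 0.67.
- Open, post-meal rise, recovery at 200 minutes: 60/200 = 0.30.
- Open, never recovers, lowest value still the 210 at 60 minutes: 30/60 = 0.50.

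The meal error can go up, down or nowhere.

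**Step 4: effect on the comparison.** Suppose a failed-set window should score zero but scores 0.48 to 0.82, and the share of such windows differs between treatments by d (assumed). The shift in the mean difference is d × 0.48 to d × 0.82: about 0.005 to 0.008 mg/dL/min at d = 1%, 0.024 to 0.041 at 5%, and 0.048 to 0.082 at 10%.

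SAP 9.3 also plans a rate per unit of insulin. If the divisor is the index bolus alone, which the SAP does not state, other insulin would act on the numerator but be missing from the divisor.

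**The case against.** The strongest reply concerns syringe doses. A reader might infer that a syringe rescue never closes the window. Suppose glucose is 300 at the pump bolus and 310 at 60 minutes, a syringe dose and new set follow at 60 minutes, and glucose reaches 180 at 220 minutes. The score would seem to be (300 − 180)/220 = 0.55 mg/dL/min. The documents do not support that as the normal outcome. All non-meal corrections are to be logged, and the route answer attaches to the first bolus, here the pump bolus. The later syringe dose would usually be untagged, count as pump-delivered and survive Step 2, so Step 5 would censor at 60 minutes. The 0.55 arises only if the syringe dose is itself tagged and Step 2 is applied strictly first, or if it is not logged. This part of the reply stands: the syringe question is an ambiguity, not a clear omission.

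The set-change gap is also limited. A logged correction after the change already censors, windows that recovered earlier are untouched, and Protocol 5.1 expects unexplained hyperglycemia to be uncommon. That restricts how often the gap matters but does not supply the missing rule.

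On meals, the reply is that the data are thin. Carb and insulin markers are required only for breakfast, and missing 4-point SMBG values are generally not protocol deviations. The comparison with SAP 9.11 is imperfect because those variables are tabulated for breakfast, where markers exist. This stands, and it argues against making meal censoring the main rule.

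Finally, SAP 9.3 is already stricter than Protocol 10.3.3.2, which states no censoring. The endpoint is secondary, without multiplicity control, in a trial not powered for superiority or non-inferiority. That sets the weight of the point; it does not remove it.

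**Conclusion.** The point holds as a cheap improvement. SAP 9.3 has no closing rule for an infusion set change or for a following meal or meal bolus, the on-pump restriction does not supply one, and the handling of a tagged syringe dose is open to two readings. Glucose changes with other causes can therefore be scored to the index bolus.

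The size is unknown. In the assumed failed-set window, a bolus with no effect scores 0.48 to 0.82 mg/dL/min; the effect on the treatment difference depends on a between-treatment imbalance in such windows that the documents do not quantify. The primary analysis and sample size are unaffected.

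Two stronger readings are not supported. One is that the rule systematically credits falls to the pump bolus; for meals, the assumed example moves from 0.50 to 0.67 or to 0.30. The other is that about half of all windows are contaminated. With lunch assumed at 12:30 and dinner at 19:00, the times 08:30–12:30 and 15:00–19:00 give 8 of 16 waking hours (07:00–23:00) within 4 hours before a meal. That figure rests on assumed meal times and evenly spread corrections, and it ignores windows that end earlier at recovery. It is an upper bound on exposure under those assumptions, not a contamination rate.

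**What to change.** Amend SAP 9.3 before unblinding:

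1. State that Step 5 looks for a later bolus among all eCOA correction boluses, whatever the route, before the Step 2 exclusion. Drop exact-time duplicates first, so that a repeated entry does not censor at time zero.
2. Add the recorded infusion set change time as a censoring event. Table ITSI.6.4 shows these times are already in eCOA or the eCRF.
3. Keep windows with no fall before censoring, with a stated score (for example a rate of zero), so that failed boluses are not silently dropped.
4. Add a sensitivity analysis that also censors at the next recorded CGM carb or insulin marker or labelled pre-meal SMBG. State that markers are required only for breakfast and that SMBG is an incomplete proxy for meal time.
5. Report, by treatment, how many windows ended for each reason.

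The cost is SAP wording and a little more programming on data already planned, with no new procedures for patients. The downside is that some windows become shorter and move from the time-to-recovery rule to the greatest-reduction rule, a different estimator; the counts in item 5 show how often that happens.

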9.4. Incremental Area under the Glucose Curve (iAUC)

iAUC_{0-T} will be calculated as the average value of iAUC on all valid CGM days during that visit with sufficient data to calculate the iAUC_{0-T} (Section 6.12). For each day, iAUC_{0-T} will be calculated as the sum of areas of all individual trapezoids within the time frame according to the formula:

$$iAUC_{0-T} = \sum_{i=1}^k A_i = \sum_{i=1}^k \frac{(G_i - G_0) + (G_{i-1} - G_0)}{2} \Delta t_i$$

where A_i is area of the respective trapezoid, G_i is glucose concentration at a particular time, G_0 is the starting glucose concentration before the start of the meal, Δt_i is the time interval between consecutive ISIG glucose measures, which should be always 5 minutes unless missing data occur, and k is the total number of intervals within the time frame 0-T. If the intermediate time points are missing, the next available time point will be used in calculating the trapezoid area. Also since it is possible that $G_i < G_0$ or $G_{i-1} < G_0$, A_i could also be negative. G_0 , the starting glucose concentration, will be calculated as the average of the CGM values in the time window [-19, 0] mins relative to the start of the meal (at most 3 ISIG glucose measures); G_k , the last glucose concentration, is defined as the average of the CGM values in the window [0, +14] minutes relative to the last time point of the time frame (at most 2 ISIG glucose measures). For example, to calculate iAUC_{0-2hr}, G_k will be the average of the CGM values in the window [0, +14] minutes relative to the 2 hours after the start of breakfast. The derivation of each iAUC_{0-T} will require that G_0 and G_k values are both available.

9.5. Average Glucose Excursions

Average glucose excursions 0 to 1 hours and 0 to 2 hours will be calculated by averaging all excursion values within 1 or 2 hours. Excursions will be derived by subtracting glucose values by the starting glucose concentration, which is the average of the CGM values in the time window [-19, 0] mins relative to the start of the meal (at most 3 ISIG glucose measures).

9.6. Glucose in Target Ranges, Hypoglycemia- or Hyperglycemia

The percentage of time within a glucose range (target, hypo- or hyperglycemia ranges) will be calculated as the number of observations within the specified range divided by the number of observations in the time interval (e.g., 24-hour period). The duration (in minutes) within the glucose range will then be calculated as the percentage of time within the glucose range times the length of the period (24 hour, 18 hour, and 6 hour, for the periods of 24-hour, daytime or nighttime, respectively).

For example, if a patient had a total of 135 observations with glucose values ≤ 70 mg/dL (3.9 mmol/L) out of a total of 3078 observations recorded during the 24-hour period across days for Visit 8, the percentage of time spent in hypoglycemia during the 24-hour period for this patient at Visit 8 will be calculated as $135/3078 = 4.4\%$. The duration (in minutes) with hypoglycemia (glucose value ≤ 70 mg/dL [3.9 mmol/L]) during the 24-hour period for this patient at Visit 8 will be calculated as the percentage times 1440, i.e., $135/3078 * 1440 = 63.2$ minutes.

The percentage and duration in ranges within 0-1 hour, 0-2 hours and 0-3 hours after breakfast will also be derived.

9.7. Hypoglycemic/Hyperglycemic Episodes

Hypoglycemic/hyperglycemic episodes as measured by CGM data are defined as at least 10 consecutive minutes below/above the specified threshold, and determined by 3 or more consecutive CGM values meeting the criterion.

The number of distinct hypoglycemic episodes that start will be derived along with days of CGM use (Section 6.12) to calculate the rate of hypoglycemic episodes during a 24-hour period. For example, the rate of postprandial hypoglycemic episodes (≤ 70 mg/dL [3.9 mmol/L]), during the 24-hour period, will be calculated with the following steps:

- Step 1: identify all events as runs of 3 or more consecutive CGM values meeting the criterion, where the pre-marker glucose value (≤ 70 mg/dL [3.9 mmol/L]). Consecutive implies no gaps in time more than 6 minutes between measurements. Events will be identified without regard for the CGM level prior to the start of the Carb event.
- Step 2: Count the number of distinct events over the 24-hour period.
- Step 3: Calculate rate per month by multiplying count by 30/days of CGM use. Days of CGM use will be calculated as the number of observations during the 24-hour period divided by the observation supposed to be measured during the period (288 observations for the 24-hour period).

9.8. Glucose Variability

Glycemic variability will be evaluated using the notation below:

i represents a time point within a time period (a 24-hour period, daytime or nighttime)

n represents the number of time points within the time period

k represents a day within a visit

m represents number of days CGM is performed at a visit

$BG_{k,i}$ represents the glucose value at time point i on day k unless otherwise specified under MAGE definition.

